9.3.5. Outpatient data capture

Following discharge from the hospital, a Patient Diary will be used to record health care intervention, diagnosis of wound infection, dressing changes, antibiotics used and quality of life (EQ-5D-5L at day 7, 14, 21 and 30, and SF-12 at day 30). If the date of discharge is after day 7, then the relevant days that have passed whilst the participant is in hospital will be crossed off by the research team, ensuring that the participant starts to fill out the diary on the correct day. There will be no collection of health resource usage whilst the participant is in hospital.

To help with completing the diary, a member of the research team will contact the participant by telephone or text message (as dictated by participant choice) every week to provide assistance and also to arrange their outpatient review. Prior to the review at day 30, the Bluebelle wound healing questionnaire in the diary should be completed by the participant. If the day 30 review is completed in person the diary should be collected from the participant at this hospital visit. If the day 30 review is conducted remotely the participant should be reminded to post it back to the SUNRISE Trial Office.

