9.3.6. Day 30 assessment

At day 30 (assessment window: Days 30-44; with day 0 being the day of randomisation), a blinded review will take place. If an in-person wound assessment is not possible as the patient is not able to return for an outpatient or research visit to the hospital, this wound assessment is to be conducted using real-time remote video consultation. Telephone follow up assessments of the patient and their wound status can be used as a last resort. The wound will be assessed for an infection according to the CDC SSI criteria. As part of the assessment the highest Clavien-Dindo grade of wound complication that occurred since surgery will be recorded²⁶.

As part of this wound inspection, the Wound Assessment Day 30 CRF will be completed, which includes asking the participant to rate their wound pain using a 10-point visual analogue scale. The participant will also be asked to complete the Quality of Life questionnaires, EQ-5D-5L and SF-12, if they have not already done so in the Patient Diary. If no wound infection is evident then the participant will have completed the study.

Prior to undergoing the Day 30 review, the participant will have completed the Bluebelle wound healing questionnaire in the Patient Diary. This assessment will be repeated with the wound assessor as part of the Day 30 review and will allow SUNRISE to compare results with the Bluebelle questionnaire. However, if the participant remains an inpatient at the time of the Day 30 assessment, the questionnaire does not need to be completed by the patient or repeated with the wound assessor.

In order to encourage and facilitate patients to attend their in-person wound review at day 30 (where appropriate), their travel expenses in the form of taxi fares, public transport costs or parking charges will be supported.

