9.3.9. Bluebelle sub-study

The method of assessing wounds forms a crucial part of any trial investigating SSIs. The current method using CDC criteria relies on healthcare professionals evaluating the wound to diagnose an SSI. The Bluebelle study has proposed a new measure for SSI that can be undertaken by the patient to diagnose the presence of a wound infection as a research tool²⁷. This tool would, if validated, allow subsequent research to be undertaken without the need for repeated clinical assessments. The SUNRISE Trial provides an opportunity to compare the outcome of the patient delivered questionnaire with the clinical assessment using the CDC criteria. In order to assess this, participants will be asked to complete a Bluebelle questionnaire at

home prior to their Day 30 wound assessment (the questionnaire forms part of the SUNRISE Patient Diary). This will be compared to the Bluebelle questionnaire completed with the wound assessor during the Day 30 wound assessment and the primary outcome measure of an SSI according to the CDC criteria.

As part of SUNRISE, SSIs diagnosed at any assessment time points in the trial will be compared to the number of SSIs identified by a one-off Bluebelle questionnaire completed by the patient before their Day 30 wound assessment. The Bluebelle team at the Clinical Trials and Evaluation Unit (CTEU) Bristol will be given access to a limited selection of data points for them to be able to externally validate the questionnaire. Participants will be informed of this sub-study in the PIS and will be asked to provide consent for authorised individuals from the CTEU Bristol to have access to their anonymised data.

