9.4. Schedule of Assessments

Activity/CRF		Pre-theatre	In-theatre	Day 7 post-op (-2/+3 days)	Day 14 post-op (± 2 days)	Day 21 post-op (± 2 days)	Day 30 post-op (+ 14 days)	Day 30+
Patient identification and screening		On-call surgical team						
Patient consent	• Standard	Patient & Member of the research team						
	• Delayed (UK only)	Consultee/Representative & Member of the research team		Patient & Member of the research team when capacity regained				
Randomisation form		Started pre-theatre by the research team	Surgeon or member of the research team					
In-Theatre form			Ideally an operating surgeon, or member of the research team					
Wound Assessment Day 7 or on Discharge (if sooner)^{1,2}				Member of the research team				
EQ-5D-5L		Completed by the participant		Completed by the participant	Completed by the participant	Completed by the participant	Completed by the participant	
SF-12		Completed by the participant		Completed by the participant			Completed by the participant	
Patient diary				Completed daily by the participant following discharge from hospital until they undergo the Day 30 wound review				Patients to continue with a diary if they have an ongoing SSI
Bluebelle wound healing questionnaire							Completed by the participant independently, and then by the participant with a blinded member of the research team reviewing wound	
Wound Assessment Day 30¹							Completed by a blinded member of the research team as an in-person or remote (video) review	
SAE reporting			All serious adverse events by member of the research team using SAE form or wound assessment CRF if excluded from expedited reporting					Related serious adverse events only
Return to theatre form			Member of the research team for any return to theatre following patient returning to theatre					
PI Declaration form for CFR data								Completed by PI at the end of each participant's involvement

¹ Assessment of pain undertaken by a member of the research team by asking the participant and recording the response on the CRF

² Score of patient acceptability of dressing undertaken by a member of the research team by asking the participant and recording the response on the CRF

Table 1: Table of assessments. Member of the research team is a person named on the local delegation log and given the assigned duty.

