11.3. Participant completed questionnaires

Participants will complete SF-12 questionnaires at baseline, day 7 and day 30, and EQ-5D-5L questionnaires at baseline, day 7, 14, 21 and day 30.

On discharge from hospital, participants will be asked to complete a daily Patient Diary (which includes the weekly EQ-5D 5L and SF-12 questionnaires) between their discharge from hospital and their Day 30 wound review. These will be completed at home with a weekly phone call or text message from the local research team to remind the participant to complete their diary. The diary will be checked with the participant at their wound review and any missing data points will be clarified.

As part of the diary, participants will complete a Bluebelle wound healing questionnaire before seeing the research team at the Day 30 wound review. It is very important that this is completed by the participant independent from any healthcare professional. If, for any reason, participants have not completed this prior to their Day 30 wound review, they will be asked to complete it independently before the review proceeds with the research team member performing it.

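### The Day 30 CDC diagnosis is not kept independent of the Bluebelle answers it serves to validate, so their agreement may be inflated

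*Protocol*

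**What the plan says.** Section 3.2, under the trial's aims, sets up a comparison of Bluebelle with the CDC-based wound review. Section 9.3.9 says that an outside team will use the data for external validation, and defines the reference broadly: "SSIs diagnosed at any assessment time points in the trial will be compared to the number of SSIs identified by a one-off Bluebelle questionnaire".

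- **The participant's form.** It is filled in before the Day 30 review, and "the questionnaire forms part of the SUNRISE Patient Diary". Section 11.3 stresses: "It is very important that this is completed by the participant independent from any healthcare professional". A participant who has not filled it in does so alone before the review goes ahead.
- **The repeat.** Section 9.3.6: "This assessment will be repeated with the wound assessor as part of the Day 30 review". The schedule in 9.4 confirms who is present: "Completed by the participant independently, and then by the participant with a blinded member of the research team reviewing wound".
- **The diary.** Section 11.3: "The diary will be checked with the participant at their wound review and any missing data points will be clarified". Section 9.3.5 has the diary collected at an in-person review. Otherwise: "If the day 30 review is conducted remotely the participant should be reminded to post it back to the SUNRISE Trial Office".
- **Blinding.** Sections 1.2.2 and 7.5 blind the Day 30 assessor to treatment allocation. Neither mentions the questionnaire.
- **Review mode.** Section 9.3.6 prefers in-person, then video, and adds: "Telephone follow up assessments of the patient and their wound status can be used as a last resort". The Day 30 wound assessment row in 9.4 lists in-person and video only.

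**The concern.** In a validation study, the reference diagnosis should be made without knowledge of the index-test result. The protocol guards one direction: the participant answers without help from a professional. It does not guard the other. The person who decides whether the CDC criteria are met goes through the same questionnaire with the participant in the same review, and nothing requires the decision to be recorded first.

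The CDC definition in 9.1 includes a clinician's diagnosis of SSI, which is a judgement that the answers could sway. The review falls at Days 30 to 44 but must classify infection within 30 days, so part of it depends on history.

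At stake is the credibility of the validation. Section 9.3.9 hopes that the tool will let later research do without repeated clinical assessment. Analysis can stratify the results, but it cannot recover the diagnosis that would have been made without the answers in view.

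**Working it through.** **The protocol's own figures.** None is given for the sub-study. The only sample size is for the treatment comparison (14.1): the pooled two-proportion formula gives 335 per group against the stated 336, and 672/0.8 = 840. Nothing below depends on it.

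**Passages side by side**

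1. The index test always comes first (9.3.6, 9.3.9, 11.3).
2. The person reviewing the wound repeats it in that review (9.3.6, 9.4).
3. The diary with the participant's form is checked at the review, with no exemption for the Bluebelle pages (9.3.9, 11.3).
4. Blinding covers allocation only (1.2.2, 7.5), and no order of recording is stated.

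Taken together, these leave the Day 30 reference open to the index-test answers.

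**Illustration of size.** The inputs are assumptions, not protocol values. The SSI rate is 20%, the midpoint of the design rates in 14.1: (25% + 15%)/2. True sensitivity is 80% and true specificity 90%. Per 100 participants, with Bluebelle judged against the reference: TP = 20 × 0.80 = 16, FN = 4, FP = 80 × 0.10 = 8, TN = 72.

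Let a share f of discordant reference calls be changed to match the questionnaire:

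- TP' = TP + f·FP and FP' = (1 − f)·FP
- FN' = (1 − f)·FN and TN' = TN + f·FN
- kappa = (po − pe)/(1 − pe), where po is observed and pe chance agreement

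At f = 0: po = 0.88, pe = 0.24 × 0.20 + 0.76 × 0.80 = 0.656, and kappa = 0.224/0.344 = 0.65.

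At f = 25%: TP' = 18, FP' = 6, FN' = 3, TN' = 73. Sensitivity is 18/21 = 0.86 and specificity 73/79 = 0.92. With po = 0.91 and pe = 0.24 × 0.21 + 0.76 × 0.79 = 0.6508, kappa = 0.2592/0.3492 = 0.74.

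Moving FN to TN means withdrawing an SSI because Bluebelle was negative. An SSI already on record would stand, so a milder variant moves only FP to TP. At f = 25% this gives TP' = 18, FP' = 6, FN = 4, TN = 72. Sensitivity is 18/22 = 0.82, specificity 72/78 = 0.92, and kappa = (0.90 − 0.6456)/0.3544 = 0.72.

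| f | Both directions: sens / spec / kappa | SSI calls added only: sens / spec / kappa |
|---|---|---|
| 0 | 0.80 / 0.90 / 0.65 | 0.80 / 0.90 / 0.65 |
| 10% | 0.82 / 0.91 / 0.69 | 0.81 / 0.91 / 0.68 |
| 25% | 0.86 / 0.92 / 0.74 | 0.82 / 0.92 / 0.72 |
| 50% | 0.91 / 0.95 / 0.83 | 0.83 / 0.95 / 0.78 |

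With both directions and f from 0 to 50%, kappa goes from 0.61 to 0.81 at a 15% SSI rate and from 0.68 to 0.84 at 25%.

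**The opposite direction.** Suppose the reference misses SSIs independently of the questionnaire, as a telephone review might. If 10% are missed: TP 14.4, FN 3.6, FP 9.6, TN 72.4, and kappa = (0.868 − 0.6664)/0.3336 = 0.60. If 30% are missed: TP 11.2, FN 2.8, FP 12.8, TN 73.2, and kappa = (0.844 − 0.6872)/0.3128 = 0.50. This error lowers agreement.

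**The case against.** The strongest reply is that much of the comparison is protected, and several points of it stand.

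- A reader might infer that Bluebelle has no independent reference at all. That is not so. The reference takes in SSIs found at Day 7 or discharge, before the questionnaire is completed, and the participant's own form must be completed unaided.
- A reader might infer that the assessor personally checks the diary. Section 11.3 does not name the checker, and after a remote review the diary is posted. The diary route and the telephone route therefore largely do not coincide.
- Infections recorded in the diary are not merely symptom scores in another form. Section 9.3.5 has it record healthcare contacts and diagnoses of wound infection, and a clinician's diagnosis is itself a CDC criterion.
- Section 11.3 has a specific rule for a Bluebelle form not yet completed. The tension with the clarification step is therefore limited to missing items on a part-completed form.
- Telephone review is a last resort, its share is unknown, and its errors may reduce agreement.
- Bluebelle is not a primary or secondary outcome. Section 11.2 says that CRF guidance will cover which forms are completed and when, so that guidance could set the order.

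None of this removes the central point. The repeat by the person reviewing the wound is explicit in both 9.3.6 and 9.4 and does not depend on the diary check. CRF guidance might settle the order, but the protocol does not require it.

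**Conclusion.** The concern holds in a limited form. For the Bluebelle comparison, the protocol does not keep the Day 30 CDC diagnosis independent of the Bluebelle answers, so agreement between the two may be inflated by review bias. The size is unknown. The range in kappa, from 0.65 up to between 0.68 and 0.83, rests wholly on assumed accuracy and assumed shares of influenced calls.

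Two stronger conclusions are not supported. The documents do not show that agreement *is* inflated overall, since independent telephone error, or an SSI that healed before a one-off questionnaire, would pull the other way. Nor do they show bias in the treatment comparison: the Day 30 assessor is blinded to allocation and the same procedure applies in both arms.

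This is a cheap improvement to a stated aim, not a threat to the main result.

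**What to change.** 1. In 9.3.6 and 11.3, require the CDC section of the Day 30 form to be completed before the assessor sees the participant's Bluebelle pages or repeats the questionnaire.
2. In 11.3, exempt the Bluebelle pages from the step in which missing diary items are clarified.
3. Keep the reference as SSI at any assessment time point, as 9.3.9 has it. Dropping diary-reported clinician diagnoses would conflict with that section and could count true cases as non-cases. As a sensitivity analysis, report agreement by review mode (in-person, video, telephone) and by source and timing of diagnosis.
4. Reconcile 9.3.6 with 9.4 on whether a telephone review is permitted.

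**Cost.** The existing visit and form are reordered, with no new procedure or staff. Slightly more Bluebelle items will be missing. The assessor-led Bluebelle will be completed with the CDC decision already known, so it cannot serve as an independent test against that decision; the participant's own form can.

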9.3.7. Assessments after 30 days

A small number of participants will have an SSI that has not healed (ongoing SSI) at the Day 30 review. These participants will be given a second Patient Diary (Continuing involvement) and asked to complete it. If the patient is followed up remotely, the patient will be sent a Patient Diary (Continuing involvement) through the post. When the wound has healed, indicated by discharge from district nursing care or from the care of the treating clinician, the participant can stop using the Patient Diary and return it to the research team or SUNRISE Trial Office. A very small proportion of these participants will have a long term, ongoing wound infection. It is important to identify and collect data on this small number of participants as they will incur a significant amount of healthcare costs and influence the health economics analysis. Data on interventions for wound infections, contact with healthcare professionals and ongoing wound care management is very important during this part of the data collection. Participants will be asked to continue with the diary until their wound heals or the trial follow-up period (participants may need several diaries). The research team looking after the participant will liaise with the participant to find the most practical way of managing the need for ongoing diaries. This may mean exchange of diaries via post, or when the participant visits the hospital for another reason.

9.3.8. Patient and healthcare professional acceptability of intervention

In order to assess the acceptability of the SUNPD, participants and healthcare professionals will be asked for their opinion on dressings that were used. All participants (including those allocated to Surgeon's preference of dressing) will be asked to assess the dressing that they had applied. Participants will be asked to rate the acceptability of their dressing at their day 7 or discharge assessment (whichever is first) using a 10-point visual analogue scale.

In the UK only, healthcare professionals will be asked for their assessment of acceptability via an online questionnaire. Surgeons, ward nurses and research nurses will be asked to provide feedback.

9.3.9. Bluebelle sub-study

The method of assessing wounds forms a crucial part of any trial investigating SSIs. The current method using CDC criteria relies on healthcare professionals evaluating the wound to diagnose an SSI. The Bluebelle study has proposed a new measure for SSI that can be undertaken by the patient to diagnose the presence of a wound infection as a research tool²⁷. This tool would, if validated, allow subsequent research to be undertaken without the need for repeated clinical assessments. The SUNRISE Trial provides an opportunity to compare the outcome of the patient delivered questionnaire with the clinical assessment using the CDC criteria. In order to assess this, participants will be asked to complete a Bluebelle questionnaire at

home prior to their Day 30 wound assessment (the questionnaire forms part of the SUNRISE Patient Diary). This will be compared to the Bluebelle questionnaire completed with the wound assessor during the Day 30 wound assessment and the primary outcome measure of an SSI according to the CDC criteria.

As part of SUNRISE, SSIs diagnosed at any assessment time points in the trial will be compared to the number of SSIs identified by a one-off Bluebelle questionnaire completed by the patient before their Day 30 wound assessment. The Bluebelle team at the Clinical Trials and Evaluation Unit (CTEU) Bristol will be given access to a limited selection of data points for them to be able to externally validate the questionnaire. Participants will be informed of this sub-study in the PIS and will be asked to provide consent for authorised individuals from the CTEU Bristol to have access to their anonymised data.

9.4. Schedule of Assessments

Activity/CRF		Pre-theatre	In-theatre	Day 7 post-op (-2/+3 days)	Day 14 post-op (± 2 days)	Day 21 post-op (± 2 days)	Day 30 post-op (+ 14 days)	Day 30+
Patient identification and screening		On-call surgical team						
Patient consent	• Standard	Patient & Member of the research team						
	• Delayed (UK only)	Consultee/Representative & Member of the research team		Patient & Member of the research team when capacity regained				
Randomisation form		Started pre-theatre by the research team	Surgeon or member of the research team					
In-Theatre form			Ideally an operating surgeon, or member of the research team					
Wound Assessment Day 7 or on Discharge (if sooner)^{1,2}				Member of the research team				
EQ-5D-5L		Completed by the participant		Completed by the participant	Completed by the participant	Completed by the participant	Completed by the participant	
SF-12		Completed by the participant		Completed by the participant			Completed by the participant	
Patient diary				Completed daily by the participant following discharge from hospital until they undergo the Day 30 wound review				Patients to continue with a diary if they have an ongoing SSI
Bluebelle wound healing questionnaire							Completed by the participant independently, and then by the participant with a blinded member of the research team reviewing wound	
Wound Assessment Day 30¹							Completed by a blinded member of the research team as an in-person or remote (video) review	
SAE reporting			All serious adverse events by member of the research team using SAE form or wound assessment CRF if excluded from expedited reporting					Related serious adverse events only
Return to theatre form			Member of the research team for any return to theatre following patient returning to theatre					
PI Declaration form for CFR data								Completed by PI at the end of each participant's involvement

¹ Assessment of pain undertaken by a member of the research team by asking the participant and recording the response on the CRF

² Score of patient acceptability of dressing undertaken by a member of the research team by asking the participant and recording the response on the CRF

Table 1: Table of assessments. Member of the research team is a person named on the local delegation log and given the assigned duty.

9.5. Participant Withdrawal

Informed consent is defined as the process of learning the key facts about a clinical trial before deciding whether or not to participate. It is a continuous and dynamic process; participants should be asked about their ongoing willingness to continue participation and this documented in the participant's medical notes.

Participants should be aware at the beginning of the trial that they can freely withdraw (discontinue participation) from the trial (or part of) at any time.

Types of withdrawal as defined are:

- The participant would like to withdraw from trial treatment, but is willing to be followed up in accordance with the schedule of assessments and if applicable using any central UK NHS or Australian healthcare bodies for long-term outcomes (i.e. the participant has agreed that data can be collected and used in the trial analysis)
- The participant would like to withdraw from trial treatment and does not wish to attend trial visits/assessments in accordance with the schedule of assessments but is willing to be followed up at standard clinic visits and if applicable using any central UK NHS or Australian healthcare bodies for long-term outcomes (i.e. the participant has agreed that data can be collected at standard clinic visits and used in the trial analysis, including data collected as part of long-term outcomes)
- The participant would like to withdraw from trial treatment and is not willing to be followed up in any way for the purposes of the trial and for no further data to be collected (i.e. only data collected prior to the withdrawal can be used in the trial analysis)

The details of withdrawal (date, reason and type of withdrawal) should be clearly documented in the source data and a Patient Discontinuation Form completed. Primary outcome data (SSI rate at 30 days) from participants who have withdrawn from the trial will be derived where possible from routine outpatient follow-up appointments or hospital records where necessary. The impact of this on the study findings will be explored in a sensitivity analysis.

